9.6 Safety Analyses

In the safety analyses, data up to the end of study will be summarized in the final analysis. The safety analyses will be based on the safety analysis set.

9.6.1 Adverse Events

The Medical Dictionary for Regulatory Activities (MedDRA) version **26.0** or later will be used to code all adverse events to a system organ class and a preferred term. The severity of each event will be graded using Common Terminology Criteria for Adverse Events (CTCAE) version 5.

The subject incidence of adverse events will be summarized for all treatment-emergent adverse events, serious adverse events, adverse events leading to withdrawal of IP, fatal adverse events, treatment-related adverse events, treatment-related serious adverse events, treatment-related adverse events leading to withdrawal of IP, treatment-related fatal adverse events **and adverse events of interest**. Subject incidence of treatment-emergent adverse events identified by COVID-19 standardized MedDRA queries and serious adverse events occurring on or after the COVID-19 infection will also be summarized.

Subject incidence of all treatment-emergent adverse events, serious adverse events, adverse events leading to withdrawal of IP, and fatal adverse events will be tabulated by system organ class in alphabetical order and preferred term in descending order of frequency.

Subject incidence of events of interest (standardized MedDRA queries [SMQ] and/or Amgen Medical Queries [AMQ]) will also be summarized according to their categories, preferred term and severity grade. The events of interests will include but not limited to hypersensitivity (SMQ), injection site reactions (AMQ), infections (infections and infestations system organ class) and malignancy (SMQ).

Summaries of treatment-emergent and serious adverse events will be tabulated by system organ class, preferred term and grade. An overall summary of adverse events by severity grade will be provided.

9.6.2 Laboratory Test Results

Selected clinical laboratory test results, change and percent change from baseline will be summarized over time by treatment arm. In addition, shift tables from baseline to the worst on-study laboratory toxicity based on the CTCAE version 5, will be presented.

Table 9-4 Selected Safety Laboratory Tests

Chemistry	Hematology	Urinalysis
Creatinine	RBC	Protein/creatinine ratio
Total bilirubin	Hemoglobin	WBC
AST (SGOT)	Hematocrit	RBC
ALT (SGPT)	MCV	
C-reactive Protein	Reticulocytes	Platelets
	WBC	
	Differential	
	
 • Eosinophils • Basophils • Lymphocytes 	

ALT = alanine aminotransferase; AST = aspartate aminotransferase; MCV = mean corpuscular volume; RBC = red blood cell count; SGOT = serum glutamic-oxaloacetic transaminase; SGPT = serum glutamic-pyruvic transaminase; WBC = white blood cell count

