215 Current or previous treatment with a biologic agent **with immunosuppressive/immunomodulatory activity** for SLE or other conditions as follows: rituximab within 6 months prior to screening; **abatacept**, belimumab, and anifrolumab within the past 3 months prior to screening; other biologics within less than 5 drug half-lives **or within the period of pharmacodynamic activity, when relevant**, prior to screening.

216 Subjects who have received intra-articular, intra-lesional, or systemic corticosteroid injections within 6 weeks prior to screening.

217 Subjects who have received live vaccines within 5 weeks prior to screening, or plan to receive live vaccines during the treatment period and up to 16 weeks after **last administration** of the **investigational product**.

Prior/Concurrent Clinical Study Experience

218 Currently receiving treatment in another investigational device or drug study.

219 Ending a treatment with an investigational drug or investigational device less than 5 **drug** half-lives from the last dose of the investigational **product or within the period of its pharmacodynamic activity when relevant**, at screening.

220 Subject previously randomized in this study.

Diagnostic Assessments

221 Presence of laboratory abnormalities at screening including the following:

- Aspartate aminotransferase (AST) or alanine aminotransferase (ALT) > 2 x upper limit of normal (ULN)
- Serum total bilirubin (TBL) \geq 1.2 mg/dL (\geq 26 μ mol/L) **except for Gilbert's Syndrome**
- Hemoglobin < 8 g/dL (< 80 g/L)
- Platelet count < 75,000/mm³ (75×10^9 /L)
- White blood cell count < 2000 cells/mm³ (2×10^9 /L)
- Absolute neutrophil count (ANC) < 1,000/mm³ (1×10^9 /L)
- Calculated glomerular filtration rate of \leq 30 mL/min/1.73 m² using the Modification of Diet in Renal Disease (MDRD) formula

222 Any other laboratory abnormality, which in the opinion of the investigator or Central Review Team, poses a safety risk, will prevent the subject from completing the study or will interfere with the interpretation of the study results, or might cause the study to be detrimental to the subject.

Other Exclusions

223 Female subject is pregnant or breastfeeding or planning to become pregnant or breastfeed during treatment and for at least 10 additional weeks after the last dose of investigational product.

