10.3.2.3.3 Laboratory Test Results

Clinical laboratory test results and change from baseline will be summarized over time by each treatment group. In addition, shift tables, from baseline to the worst on-study laboratory toxicity based on the latest version of CTCAE grading, will be presented.

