12.2 Appendix 2. Clinical Laboratory Tests

Additional tests may be performed at any time during the study as determined necessary by the investigator or required by local regulations.

Table 12-1. Analyte Listing^a

Central Laboratory: Chemistry	Central Laboratory: Coagulation	Central Laboratory: Urinalysis	Central Laboratory: Hematology	Central Laboratory: Other Labs
Sodium	PT/INR	Protein/creatinine ratio	Central Laboratory:	Central Laboratory:
Potassium	aPTT	Specific gravity	RBC	Hep B surface antigen
Chloride	Fibrinogen ^b	pH	Nucleated RBC	Hep B core antibody
Bicarbonate	D-dimer ^b	Blood	Hemoglobin	Hep B virus DNA ^c
Total protein		Protein	Hematocrit	Hep C antibody
Albumin		Glucose	MCV	Hep C virus RNA ^d
Calcium		Bilirubin	MCH	Antinuclear antibody
Adjusted calcium		WBC	MCHC	
Magnesium		RBC	RDW	
Phosphorus		Epithelial cells	Reticulocytes	HIV antibody
Glucose		Bacteria	Platelets	
BUN or Urea		Casts	WBC	
Creatinine		Crystals	Differential	
Uric acid			• Bands/stabs	Serum pregnancy test
Total bilirubin			• Eosinophils	
Direct bilirubin			• Basophils	
ALP			• Lymphocytes	
LDH			• Monocytes	
AST (SGOT)			• Total neutrophils	
ALT (SGPT)			• Segmented neutrophils	
Creatinine clearance by MDRD			Local Laboratory:	QuantiFERON®-TB ^f
GGT			Erythrocyte sedimentation rate	Local Laboratory:
C-reactive protein				Urine Pregnancy
Total Cholesterol				T-spot ^f
HDL				FSH ^g
LDL				Coombs test ^h
Triglycerides				
Creatinine Phosphokinase				

Footnotes defined on next page

[REDACTED] ALP = alkaline phosphatase; ALT = alanine aminotransferase; [REDACTED] aPTT = activated partial thromboplastin time;

AST = aspartate aminotransferase; BUN = blood urea nitrogen; FSH = follicle stimulating hormone; GGT = gamma glutamyl transpeptidase; HDL = high density lipoprotein; Hep = hepatitis; HIV = Human Immunodeficiency Virus; [REDACTED] INR = international normalized ratio; LDH = lactate dehydrogenase; LDL = low density lipoprotein; MCH = mean corpuscular hemoglobin; MCHC = mean corpuscular hemoglobin concentration; MCV = mean corpuscular volume; MDRD = Modification of Diet in Renal Disease; PD = pharmacodynamic; PK = pharmacokinetic; PT = prothrombin time; PTT = partial thromboplastin time; RBC = red blood cell count; RDW = Red cell distribution width; SGOT = serum glutamic-oxaloacetic transaminase; SGPT = serum glutamic-pyruvic transaminase; WBC = white blood cell count

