- Wilson's disease and hemochromatosis
- Nonalcoholic fatty liver disease including steatohepatitis
- Non-hepatic causes (eg, rhabdomyolysis, hemolysis)

If investigational product(s) is/are withheld, the subject is to be followed for possible drug-induced liver injury (DILI) according to recommendations in the last section of this appendix.

Rechallenge may be considered if an alternative cause for impaired liver tests (ALT, AST, ALP) and/or elevated TBL, is discovered and the laboratory abnormalities resolve to normal or baseline (see next section in this appendix).

Table 12-2. Conditions for Withholding and/or Permanent Discontinuation of Amgen Investigational Product and Other Protocol-required Therapies Due to Potential Hepatotoxicity

Analyte	Temporary Withholding	Permanent Discontinuation
TBL	> 3x ULN at any time	> 2x ULN OR
INR	--	> 1.5x (for subjects not on anticoagulation therapy) AND
AST/ALT	> 8x ULN at any time > 5x ULN but < 8x ULN for \geq 2 weeks > 5x ULN but < 8x ULN and unable to adhere to enhanced monitoring schedule > 3x ULN with clinical signs or symptoms that are consistent with hepatitis (such as right upper quadrant pain/tenderness, fever, nausea, vomiting, and jaundice)	In the presence of no important alternative causes for elevated AST/ALT and/or TBL values > 3x ULN (when baseline was < ULN)
ALP	> 8x ULN at any time	--

ALP = alkaline phosphatase; ALT = alanine aminotransferase; AST = aspartate aminotransferase; INR = international normalized ratio; TBL = total bilirubin; ULN = upper limit of normal

Criteria for Rechallenge of Amgen Investigational Product and Other Protocol-required Therapies After Potential Hepatotoxicity

The decision to rechallenge the subject is to be discussed and agreed upon unanimously by the subject, investigator, and Amgen.

If signs or symptoms recur with rechallenge, then Amgen 570 is to be permanently discontinued. Subjects who clearly meet the criteria for permanent discontinuation (as described in [Table 12-2](#)) are never to be rechallenged.

Drug-induced Liver Injury Reporting and Additional Assessments

Reporting

To facilitate appropriate monitoring for signals of DILI, cases of concurrent AST or ALT and TBL and/or INR elevation, according to the criteria specified in the above, require the following:

- The event is to be reported to Amgen as a serious adverse event within 24 hours of discovery or notification of the event (ie, before additional etiologic investigations have been concluded)

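### The by-visit laboratory summaries in SAP 9.6.2 leave out total neutrophils, ALP and INR, and the SAP does not say whether its CTCAE shift tables cover them

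*SAP*

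**What the plan says.** Protocol 10.3.2.3.3 plans: "Clinical laboratory test results and change from baseline will be summarized over time by each treatment group". It adds shift tables to the worst on-study CTCAE grade and limits neither output to particular tests.

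SAP 9.6.2 narrows the first output: "Selected clinical laboratory test results, change and percent change from baseline will be summarized over time by treatment arm". The list is headed "Table 9-4 Selected Safety Laboratory Tests". For white-cell types it gives only "Eosinophils • Basophils • Lymphocytes". Its chemistry column has creatinine, total bilirubin, AST, ALT and C-reactive protein. It has no coagulation column. A second sentence in SAP 9.6.2 then says that "shift tables from baseline to the worst on-study laboratory toxicity based on the CTCAE version 5, will be presented", without referring to Table 9-4.

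Protocol Table 12-1 lists ALP under chemistry, PT/INR under coagulation and "Total neutrophils" under hematology. Protocol Table 12-2 (Section 12.7) uses ALP for temporary withholding and INR, combined with AST/ALT, for permanent discontinuation. Exclusion criterion 221 includes "Absolute neutrophil count (ANC) < 1,000/mm³".

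SAP Section 1 says that the scope was reduced after the futility stop. SAP Section 10 lists three key changes: later interim analyses, some exploratory endpoints and statistical comparisons. It does not mention laboratory tests.

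**The concern.** Laboratory changes of clinical significance are part of a secondary safety endpoint in both documents. After the futility stop, the SAP drops treatment comparisons and reports efficacy descriptively, so the description of safety by arm is one of the main things the final analysis can deliver.

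The selection in Table 9-4 is hard to explain from the protocol. It keeps basophils and eosinophils but not neutrophils, the one differential count with an eligibility limit. It keeps AST, ALT and total bilirubin but not the other two analytes in the protocol's liver table. A gradual drift by arm in neutrophils or ALP, below the level at which an investigator calls it clinically significant, is what by-visit summaries are meant to show. As planned, they would not show it for these tests.

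**Working it through.** No sample size, power or error-rate figure is involved. The check compares lists and then asks whether other planned outputs fill the gap.

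**1. Count of analytes.** Inputs are Protocol Table 12-1 (central chemistry, coagulation, hematology and urinalysis) and SAP Table 9-4.

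| Panel | Protocol Table 12-1 | SAP Table 9-4 | Not in Table 9-4 |
|---|---|---|---|
| Chemistry | 28 | 5 | 23, including ALP |
| Coagulation | 4 | 0 | 4, including PT/INR |
| Hematology | 18 | 10 | 8, including total and segmented neutrophils |
| Urinalysis | 13 | 3 | 10 |
| Total | 63 | 18 | 45 |

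63 − 18 = 45, and 45/63 = 71%. Most of the 45 are reasonable to leave out of a shortened report. Two of the four coagulation tests (fibrinogen and D-dimer) are done only in suspected liver injury. The point concerns three tests, not the 45.

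**2. Liver table.** Protocol Table 12-2 has four analyte rows: total bilirubin, INR, AST/ALT and ALP. Table 9-4 keeps total bilirubin and AST/ALT, and omits INR and ALP.

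**3. Differential count.** Table 12-1 lists seven white-cell types: bands, eosinophils, basophils, lymphocytes, monocytes, total neutrophils and segmented neutrophils. Table 9-4 keeps three. Neutrophils cannot be recovered by subtraction. WBC minus eosinophils, basophils and lymphocytes leaves neutrophils and monocytes together, and monocytes are omitted too.

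**4. Shift tables.** In SAP 9.6.2 the restriction to selected tests stands in the over-time sentence only. The shift-table sentence that follows has no such restriction, nor does its counterpart in Protocol 10.3.2.3.3. A programmer could run the shifts on all gradable tests or on Table 9-4 alone; the text allows both.

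**5. Other outputs.** SAP 9.1 says that clinically significant laboratory changes will be summarised descriptively, but the SAP gives no definition or separate method for this outside 9.6.2. SAP 9.6.1 tabulates adverse events by preferred term and grade. Under Protocol 9.2.4, however, abnormal values that the investigator judges not clinically significant are generally not recorded as adverse events, and where applicable the clinical consequence is recorded instead of the laboratory finding. The adverse event tables therefore catch the serious end of the range and do not replace summaries of the values.

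**The case against.** Much can be said for the plan as it stands.

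- The important individual cases are captured elsewhere. Laboratory changes that need treatment or a change of therapy are adverse events (Protocol 9.2.4). Concurrent AST or ALT elevation with raised bilirubin and/or INR must be reported as a serious adverse event within 24 hours (Protocol 12.7). This stands, but it covers cases above a threshold and not the distribution by arm.
- The selection has some rationale. The toxicology summary in Protocol 3.4 reports raised reticulocytes and red cell mass and lymphoid effects, and Table 9-4 keeps the matching tests. The passages compared here show no neutrophil, ALP or INR signal for this product. This explains what was kept; it does not explain the omissions.
- The SAP announces a reduced scope and calls its Section 10 list key changes. The narrowing is therefore not itemised, rather than concealed. However, futility is an efficacy finding and does not by itself account for a shorter safety table.
- The layout of Table 9-4 is disturbed in the text available to us (platelets falls under urinalysis). Its footnote defines neither ALP nor INR, which supports their absence. Neutrophils need no abbreviation, so for them the finding rests on the printed list alone. The SAP abbreviation list still defines ALP and INR, which may be left over.

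Stronger readings are tempting and go too far. A reader might infer that neutropenia and liver signals will not be shown by arm at all. The open shift-table sentence, the adverse event tables and the retained WBC, AST, ALT and bilirubin rows do not support that. A reader might also infer that the protocol promised every laboratory test; its wording is unrestricted but does not say so. Nor does the protocol make ALP or INR a free-standing discontinuation criterion: ALP is for withholding only, and INR counts only with AST/ALT. Finally, inclusion criterion 105 does not put every subject on azathioprine, mycophenolate or methotrexate, because one listed treatment such as an antimalarial is enough.

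**Conclusion.** The point holds for the by-visit summaries. Under SAP 9.6.2 as written, values and changes over time for total neutrophils, ALP and INR will not be summarised by arm, although the protocol plans such summaries without restriction and all three tests are collected. Coverage by the CTCAE v5 shift tables is unclear, and the SAP should settle it.

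The effect is limited to the description of safety in the final report. No efficacy result, estimand, analysis set or error rate changes. The conclusion assumes that Table 9-4 has no row hidden by its disturbed layout; the sponsor can confirm this at once from the source file.

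**What to change.** Add total neutrophils, ALP and INR to Table 9-4, and state in SAP 9.6.2 that the CTCAE v5 shift tables include them. If the shorter list is intended, itemise it in SAP Section 10 with the reason.

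For INR, also confirm the analysis visit window. The headings in SAP Appendix D visibly name chemistry, urinalysis and hematology but not coagulation, though parts of them are redacted.

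The cost is a few more rows in standard tables and one or two sentences. No new data, visits or tests are needed, and no clinical rule changes.

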9.6.3 Vital Signs

The actual value, change and percent change from baseline in vital signs will be summarized over time by treatment arm for systolic/diastolic blood pressure, heart rate, respiratory rate, and temperature.

9.6.4 Physical Measurements

The actual value, change and percent change from baseline in weight will be summarized by treatment arm by scheduled visit.

9.6.5 Exposure to Investigational Product (IP)

Descriptive statistics will be produced to describe the exposure to IP by treatment arm. Summary statistics will be provided for the total dose received, and total duration of IP exposure by treatment arm.

9.6.6 Exposure to Other Protocol-required Therapy

Other protocol-required therapies for this study are immunomodulators and immunosuppressants, OCS, NSAIDs, topical corticosteroids and topical calcineurin inhibitors and anti-proteinuria agents.

The baseline exposure to OCS and immunomodulators/immunosuppressants will be summarized using descriptive statistics (number and percentages).

http://ctep.cancer.gov/protocolDevelopment/electronic_applications/ctc.htm

Appendix B. SLE Assessment Forms/Instruments**HSLEDAI**

The hSLEDAI score is computed as sum of the score across the descriptors.

Weight	Score	Descriptor	Definition
8		Seizure	Recent onset, exclude metabolic, infectious or drug causes
8		Psychosis	Altered ability to function in normal activity due to severe disturbance in the perception of reality. Include hallucinations, incoherence, marked loose associations, impoverished thought content, marked illogical thinking, bizarre, disorganized or catatonic behavior. Exclude uremia and drug causes
8		Organic brain syndrome	Altered mental function with impaired orientation, memory, or other intellectual function, with rapid onset and fluctuating clinical features, inability to sustain attention to environment, plus at least two of the following: perceptual disturbance, incoherent speech, insomnia or daytime drowsiness, or increased or decreased psychomotor activity. Exclude metabolic, infection, or drug causes.
8		Visual disturbance	Retinal changes of SLE. Include cystoid bodies, retinal hemorrhages, serous exudate or hemorrhages in the choroid, optic neuritis, scleritis or episcleritis. Exclude hypertension, infection, or drug causes.
8		Cranial nerve disorder	New onset of sensory or motor neuropathy involving cranial nerves.

8		Lupus headache	Severe, persistent headache; may be migrainous, but must be non-responsive to narcotic analgesia.
8		CVA	New onset of cerebrovascular accident(s). Exclude arteriosclerosis.
8		Vasculitis	Ulceration, gangrene, tender finger nodules, periungual infarction, splinter hemorrhages, or biopsy or angiogram proof of vasculitis.
4		Arthritis	>2 joints of hands and wrists with signs of inflammation (i.e., tenderness and swelling or effusion)
4		Myositis	Proximal muscle aching/weakness, associated with elevated creatinine phosphokinase/aldolase or electromyogram changes or a biopsy showing myositis.
4		Urinary casts	Heme-granular or red blood cell casts
4		Hematuria	> 5 red blood cells/high power field. Exclude stone, infection, or other cause.
4		Proteinuria	More than 0.5 gram/24 hours.
4		Pyuria	> 5 WBC/high power field. Exclude infection.
2		Rash	Inflammatory type rash.
2		Alopecia	Abnormal, patchy or diffuse loss of hair
2		Mucosal ulcers	Oral or nasal ulcerations
2		Pleurisy	Pleuritic chest pain or pleural rub with effusion or pleural thickening.
2		Pericarditis	Classic pericardial pain and/or rub effusion with ECG confirmation
2		Low complement	Decrease in CH50, C3, or C4 below the lower limit of normal for testing laboratory
2		Increased DNA binding	Increased DNA binding above normal range for testing laboratory
1		Fever	> 38 °C. Exclude infectious cause.
1		Thrombocytopenia	< 100 x 10 ⁹ platelets / L, exclude drug causes.

1		Leukopenia	< 3 x 10 ⁹ WBC/ L, exclude drug causes.
---	--	------------	--

BILAG-2004 Index Form

BILAG2004 INDEX

Only record items due to SLE Disease Activity & assessment

Scoring: ND Not Done

- 1 Improving
- 2 Same
- 3 Worse
- 4 New

Yes/No OR Value (where indicated)
 indicate if not due to SLE activity
 (default is 0 = not present)

CONSTITUTIONAL

- 1. Pyrexia - documented > 37.5°C ()
- 2. Weight loss - unintentional > 5% ()
- 3. Lymphadenopathy/splenomegaly ()
- 4. Anorexia ()

MUCOCUTANEOUS

- 5. Skin eruption - severe ()
- 6. Skin eruption - mild ()
- 7. Anglo-oedema - severe ()
- 8. Anglo-oedema - mild ()
- 9. Mucosal ulceration - severe ()
- 10. Mucosal ulceration - mild ()
- 11. Panniculitis/Bullous lupus - severe ()
- 12. Panniculitis/Bullous lupus - mild ()
- 13. Major cutaneous vasculitis/thrombosis ()
- 14. Digital infarcts or nodular vasculitis ()
- 15. Alopecia - severe ()
- 16. Alopecia - mild ()
- 17. Peri-ungual erythema/chilblains ()
- 18. Splinter haemorrhages ()

NEUROPSYCHIATRIC

- 19. Aseptic meningitis ()
- 20. Cerebral vasculitis ()
- 21. Demyelinating syndrome ()
- 22. Myelopathy ()
- 23. Acute confusional state ()
- 24. Psychosis ()
- 25. Acute inflammatory demyelinating polyradiculoneuropathy ()
- 26. Mononeuropathy (single/multiplex) ()
- 27. Cranial neuropathy ()
- 28. Plexopathy ()
- 29. Polyradiculopathy ()
- 30. Seizure disorder ()
- 31. Status epilepticus ()
- 32. Cerebrovascular disease (not due to vasculitis) ()
- 33. Cognitive dysfunction ()
- 34. Movement disorder ()
- 35. Autonomic disorder ()
- 36. Cerebellar ataxia (isolated) ()
- 37. Lupus headache - severe unremitting ()
- 38. Headache from IC hypertension ()

MUSCULOSKELETAL

- 39. Myositis - severe ()
- 40. Myositis - mild ()
- 41. Arthritis (severe) ()
- 42. Arthritis (moderate)/Tendonitis/Tenosynovitis ()
- 43. Arthritis (mild)/Arthralgia/Myalgia ()

Weight (kg): _____

CARDIORESPIRATORY

- 44. Myocarditis - mild ()
- 45. Myocarditis/Endocarditis + Cardiac failure ()
- 46. Arrhythmia ()
- 47. New valvular dysfunction ()
- 48. Pleurisy/Pericarditis ()
- 49. Cardiac tamponade ()
- 50. Pleural effusion with dyspnoea ()
- 51. Pulmonary haemorrhage/vasculitis ()
- 52. Interstitial alveolitis/pneumonitis ()
- 53. Shrinking lung syndrome ()
- 54. Aortitis ()
- 55. Coronary vasculitis ()

GASTROINTESTINAL

- 56. Lupus peritonitis ()
- 57. Abdominal serositis or ascites ()
- 58. Lupus enteritis/colitis ()
- 59. Malabsorption ()
- 60. Protein losing enteropathy ()
- 61. Intestinal pseudo-obstruction ()
- 62. Lupus hepatitis ()
- 63. Acute lupus cholecystitis ()
- 64. Acute lupus pancreatitis ()

OPHTHALMIC

- 65. Orbital inflammation/myositis/proptosis ()
- 66. Keratitis - severe ()
- 67. Keratitis - mild ()
- 68. Anterior uveitis ()
- 69. Posterior uveitis/retinal vasculitis - severe ()
- 70. Posterior uveitis/retinal vasculitis - mild ()
- 71. Episcleritis ()
- 72. Scleritis - severe ()
- 73. Scleritis - mild ()
- 74. Retinal/choroidal vaso-occlusive disease ()
- 75. Isolated cotton-wool spots (cytoid bodies) ()
- 76. Optic neuritis ()
- 77. Anterior ischaemic optic neuropathy ()

RENAL

- 78. Systolic blood pressure (mm Hg) value ()
- 79. Diastolic blood pressure (mm Hg) value ()
- 80. Accelerated hypertension Yes/No ()
- 81. Urine dipstick protein (+=1, ++=2, +++=3) ()
- 82. Urine albumin-creatinine ratio mg/mmol ()
- 83. Urine protein-creatinine ratio mg/mmol ()
- 84. 24 hour urine protein (g) value ()
- 85. Nephrotic syndrome Yes/No ()
- 86. Creatinine (plasma/serum) μ mol/l ()
- 87. GFR (calculated) ml/min/1.73 m² ()
- 88. Active urinary sediment Yes/No ()
- 89. Active nephritis Yes/No ()

HAEMATOLOGICAL

- 90. Haemoglobin (g/dl) value ()
- 91. Total white cell count ($\times 10^9/l$) value ()
- 92. Neutrophils ($\times 10^9/l$) value ()
- 93. Lymphocytes ($\times 10^9/l$) value ()
- 94. Platelets ($\times 10^9/l$) value ()
- 95. TTP ()
- 96. Evidence of active haemolysis Yes/No ()
- 97. Coombs' test positive (isolated) Yes/No ()

Revision: 12/Jan/2007

Investigator initials: _____ Date of assessment: _____

BILAG-2004 INDEX SCORING

Scoring based on the principle of physician's intention to treat

Category	Definition
A	Severe disease activity requiring any of the following treatment: 1. systemic high dose oral glucocorticoids (equivalent to prednisolone > 20 mg/day) 2. intravenous pulse glucocorticoids (equivalent to pulse methylprednisolone \geq 500 mg) 3. systemic immunomodulators (include biologicals, immunoglobulins and plasmapheresis) 4. therapeutic high dose anticoagulation in the presence of high dose steroids or immunomodulators e.g.: warfarin with target INR 3 - 4
B	Moderate disease activity requiring any of the following treatment: 1. systemic low dose oral glucocorticoids (equivalent to prednisolone \leq 20 mg/day) 2. intramuscular or intra-articular or soft tissue glucocorticoids injection (equivalent to methylprednisolone < 500mg) 3. topical glucocorticoids 4. topical immunomodulators 5. antimalarials or thalidomide or prasterone or acitretin 6. symptomatic therapy e.g.: NSAIDs for inflammatory arthritis
C	Mild disease
D	Inactive disease but previously affected
E	System never involved

BILAG Constitutional Scoring Algorithm

Grade	Criteria
A	1. Pyrexia recorded as 2 (same), 3 (worse) or 4 (new) AND 2. Any 2 or more of the following recorded as 2 (same), 3 (worse) or 4 (new): a) Weight loss b) Lymphadenopathy/splenomegaly c) Anorexia
B	1. Pyrexia recorded as 2 (same), 3 (worse) or 4 (new) OR 2. Any 2 or more of the following recorded as 2 (same), 3 (worse) or 4 (new): a) Weight loss b) Lymphadenopathy/splenomegaly

	c) 3. BUT do not fulfil criteria for Category A
C	1. Pyrexia recorded as 1 (improving) OR 2. One or more of the following recorded as > 0: a) Weight loss b) Lymphadenopathy/Splenomegaly c) Anorexia 3. BUT does not fulfil criteria for category A or B
D	Previous involvement (i.e. A, B, C or D domain grade at any previous visits or domain previous involvement is yes)
E	No previous involvement
Missing	

BILAG Mucocutaneous Scoring Algorithm

Grade	Criteria
A	Any of the following recorded as 2 (same), 3 (worse) or 4 (new): a) Skin eruption - severe b) Angio-oedema - severe c) Mucosal ulceration - severe d) Panniculitis/Bullous lupus - severe e) Major cutaneous vasculitis/thrombosis
B	1. Any Category A features recorded as 1 (improving) OR 2. Any of the following recorded as 2 (same), 3 (worse) or 4 (new): 1. Skin eruption - mild 2. Panniculitis/Bullous lupus - mild 3. Digital infarcts or nodular vasculitis 4. Alopecia - severe
C	1. Any Category B features recorded as 1 (improving) OR 2. Any of the following recorded as > 0: a) Angio-oedema - mild b) Mucosal ulceration - mild c) Alopecia - mild d) Periungual erythema/chilblains e) Splinter haemorrhages
D	Previous involvement (i.e. A, B, C or D domain grade at any previous visits or domain previous involvement is yes)
E	No previous involvement
Missing	

BILAG Neuropsychiatric Scoring Algorithm

Grade	Criteria
A	Any of the following recorded as 2 (same), 3 (worse) or 4 (new): 1. Aseptic meningitis 2. Cerebral vasculitis 3. Demyelinating syndrome

	4. Myelopathy 5. Acute confusional state 6. Psychosis 7. Acute inflammatory demyelinating polyradiculoneuropathy 8. Mononeuropathy (single/multiplex) 9. Cranial neuropathy 10. Plexopathy 11. Polyneuropathy 12. Status epilepticus 13. Cerebellar ataxia
B	1. Any Category A features recorded as 1 (improving) OR 2. Any of the following recorded as 2 (same), 3 (worse) or 4 (new): a) Seizure disorder b) Cerebrovascular disease (not due to vasculitis) c) Cognitive dysfunction d) Movement disorder e) Autonomic disorder f) Lupus headache - severe unrelenting g) Headache due to raised intracranial hypertension
C	Any Category B features recorded as 1 (improving)
D	Previous involvement (i.e. A, B, C or D domain grade at any previous visits or domain previous involvement is yes)
E	No previous involvement
Missing	

BILAG Musculoskeletal Scoring Algorithm

Grade	Criteria
A	Any of the following recorded as 2 (same), 3 (worse) or 4 (new): a) Severe Myositis b) Severe Arthritis
B	1. Any Category A features recorded as 1 (improving) OR 2. Any of the following recorded as 2 (same), 3 (worse) or 4 (new): a) Mild Myositis b) Moderate Arthritis/Tendonitis/Tenosynovitis
C	1. Any Category B features recorded as 1 (improving) OR 2. Any of the following recorded as > 0: a) Mild Arthritis/Arthralgia/Myalgia
D	Previous involvement (i.e. A, B, C or D domain grade at any previous visits or domain previous involvement is yes)
E	No previous involvement
Missing	

BILAG Cardiorespiratory Scoring Algorithm

Grade	Criteria
A	Any of the following recorded as 2 (same), 3 (worse) or 4 (new): a) Myocarditis/Endocarditis + Cardiac failure b) Arrhythmia c) New valvular dysfunction d) Cardiac tamponade e) Pleural effusion with dyspnoea f) Pulmonary haemorrhage/vasculitis g) Interstitial alveolitis/pneumonitis h) Shrinking lung syndrome i) Aortitis j) Coronary vasculitis
B	1. Any Category A features recorded as 1 (improving) OR 2. Any of the following recorded as 2 (same), 3 (worse) or 4 (new): a) Pleurisy/Pericarditis b) Myocarditis - mild
C	Any Category B features recorded as 1 (improving)
D	Previous involvement (i.e. A, B, C or D domain grade at any previous visits or domain previous involvement is yes)
E	No previous involvement
Missing	

BILAG Gastrointestinal Scoring Algorithm

Grade	Criteria
A	Any of the following recorded as 2 (same), 3 (worse) or 4 (new): a) Peritonitis b) Lupus enteritis/colitis c) Intestinal pseudo-obstruction d) Acute lupus cholecystitis e) Acute lupus pancreatitis
B	1. Any Category A feature recorded as 1 (improving) OR 2. Any of the following recorded as 2 (same), 3 (worse) or 4 (new): a) Abdominal serositis and/or ascites b) Malabsorption c) Protein losing enteropathy d) Lupus hepatitis
C	Any Category B features recorded as 1 (improving)
D	Previous involvement (i.e. A, B, C or D domain grade at any previous visits or domain previous involvement is yes)

E	No previous involvement
Missing	

BILAG Ophthalmic Scoring Algorithm

Grade	Criteria
A	Any of the following recorded as 2 (same), 3 (worse) or 4 (new): 
 a) Orbital inflammation/myositis/proptosis b) Keratitis - severe c) Posterior uveitis/retinal vasculitis - severe d) Scleritis - severe e) Retinal/choroidal vaso-occlusive disease f) Optic neuritis g) Anterior ischaemic optic neuropathy
B	1. Any Category A features recorded as 1 (improving) OR 2. Any of the following recorded as 2 (same), 3 (worse) or 4 (new): 
 a) Keratitis - mild b) Anterior uveitis c) Posterior uveitis/retinal vasculitis - mild d) Scleritis - mild
C	1. Any Category B features recorded as 1 (improving) OR 2. Any of the following recorded as > 0: 
 a) Episcleritis b) Isolated cotton-wool spots (cystoid bodies)
D	Previous involvement (i.e. A, B, C or D domain grade at any previous visits or domain previous involvement is yes)
E	No previous involvement
Missing	

BILAG Renal Scoring Algorithm

Grade	Criteria
A	Two or more of the following providing 1, 4 or 5 is included: 
 1. Deteriorating proteinuria (severe) defined as 
 a) urine dipstick increased by ≥ 2 levels (used only if other methods of urine protein estimation not available); or b) 24-hour urine protein > 1 g that has not decreased (improved) by $\geq 25\%$ from previous visit; or c) urine protein-creatinine ratio > 100 mg/mmol that has not decreased (improved) by $\geq 25\%$; or d) urine albumin-creatinine ratio > 100 mg/mmol that has not decreased (improved) by $\geq 25\%$ 2. Accelerated hypertension 3. Deteriorating renal function (severe) defined as

	
 a) plasma creatinine > 130 μmol/l and having risen to > 130% of previous value; or b) GFR < 80 ml/min per 1.73 m² and having fallen to < 67% of previous value; or c) GFR < 50 ml/min per 1.73 m², and last time was > 50 ml/min per 1.73 m² or was not measured. 
 4. Active urinary sediment 5. Histological evidence of active nephritis within last 3 months 6. Nephrotic syndrome
B	
One of the following:
 
 1. One of the Category A feature 2. Proteinuria (that has not fulfilled Category A criteria) 
 a) urine dipstick which has risen by 1 level to at least 2+ (used only if other methods of urine protein estimation not available); or b) 24-hour urine protein \geq 0.5 g that has not decreased (improved) by \geq 25%; or c) urine protein-creatinine ratio \geq 50 mg/mmol that has not decreased (improved) by \geq 25%; or d) urine albumin-creatinine ratio \geq 50 mg/mmol that has not decreased (improved) by \geq 25% 3. Plasma creatinine > 130 μmol/l and having risen to \geq 115% but \leq 130% of previous value
C	
One of the following:
 
 1. Mild/Stable proteinuria defined as 
 a) urine dipstick \geq 1+ but has not fulfilled criteria for Category A & B (used only if other methods of urine protein estimation not available); or b) 24 hour urine protein $>$ 0.25 g but has not fulfilled criteria for Category A & B; or c) urine protein-creatinine ratio $>$ 25 mg/mmol but has not fulfilled criteria for Category A & B; or d) urine albumin-creatinine ratio $>$ 25 mg/mmol but has not fulfilled criteria for Category A & B 2. Rising blood pressure (providing the recorded values are $>$ 140/90 mm Hg) which has not fulfilled criteria for Category A & B, defined as 
 a) systolic rise of \geq 30 mm Hg; and b) diastolic rise of \geq 15mm Hg
D	Previous involvement (i.e. A, B, C or D domain grade at any previous visits or domain previous involvement is yes)
E	No previous involvement
Missing	

Since the urine albumin-creatinine ratio and 24-hour urine protein are not collected in this study, the criteria for BILAG proteinuria will be based on urine dipstick and urine protein-creatinine ration only.

BILAG Hematological Scoring Algorithm

Grade	Criteria

A	1. TTP recorded as 2 (same), 3 (worse) or 4 (new) or 2. Any of the following: a) Evidence of haemolysis and Haemoglobin < 8 g/dl b) Platelet count < 25 x 10 ⁹ /l
B	1. TTP recorded as 1 (improving) or 2. Any of the following: a) Evidence of haemolysis and Haemoglobin 8 - 9.9 g/dl b) Haemoglobin < 8 g/dl (without haemolysis) c) White cell count < 1.0 x 10 ⁹ /l d) Neutrophil count < 0.5 x 10 ⁹ /l e) Platelet count 25 - 49 x 10 ⁹ /l
C	Any of the following: a) Evidence of haemolysis and Haemoglobin ≥ 10g/dl b) Haemoglobin 8 - 10.9 g/dl (without haemolysis) c) White cell count 1 - 3.9 x 10 ⁹ /l d) Neutrophil count 0.5 - 1.9 x 10 ⁹ /l e) Lymphocyte count < 1.0 x 10 ⁹ /L f) Platelet count 50 - 149 x 10 ⁹ /l g) Isolated Coombs' test positive
D	Previous involvement (i.e. A, B, C or D domain grade at any previous visits or domain previous involvement is yes)
E	No previous Involvement.
Missing	

LLDAS

Criteria	Derivation
HSLEDAI ≤ 4 with no activity in major organ systems (renal, CNS, cardiopulmonary, vasculitis, fever) and no activity in haemolytic anaemia or gastrointestinal in BILAG	HSLEDAI score ≤ 4. proteinuria, haematuria, pyuria, urinary casts, seizure, psychosis, organic brain syndrome, cranial nerve disorder, CVA, pericarditis, pleurisy, vasculitis and fever in hSLEDAI are marked 'not present.' BILAG items 56-64 are marked as 'not present' and 96 are marked as 'No.'
No new lupus activity compared with the previous assessment	All hSLEDAI items that are 'not present' in the previous assessment are also 'not present' in the current visit.

PGA ≤ 1	PGA ≤ 1
Current prednisolone (or equivalent) dose ≤ 7.5 mg/day	Prednisone equivalent is ≤ 7.5 mg/day at the visit
Well tolerated standard maintenance doses of immunosuppressive drugs and approved biological agents (i.e. no increase or initiation of immunosuppressive drugs.)	No new or increase in immunosuppressant at the visit

